Protocol ID: MDX-DEB-001

Brief Title: Debritom - Micro Water Jet Technology and Wound Healing

Date: September 30, 2019

RESEARCH PROPOSAL

Evaluation of Micro Water Jet Technology and the Progression of Wound Healing:

A Prospective Cohort Evaluating the Efficacy of Micro Water Jet Technology in the debridement and healing of Chronic Lower Extremity Ulcers

PROTOCOL SUMMARY

Study Title

Evaluation of Micro Water Jet Technology and the Progression of Wound Healing: A Prospective Cohort Evaluating the Clinical Efficacy of Micro Water Jet Technology in the debridement and healing of Chronic Lower Extremity Ulcers.

Indication

This study will investigate the clinical efficacy of micro water jet technology in the debridement and healing of chronic lower extremity ulcers.

Objectives

The primary objective of the study is to assess the clinical efficacy of micro water jet technology in the debridement and healing of chronic lower extremity ulcers in terms of wound size, depth/extent, and percent wound reduction and healing. Additional assessments will include evaluating changes in leg rest pain score using a visual analogue scale (VAS); incidence of infection, and pain during debridement via the VAS scale as well as patient feedback regarding their debridement experience with micro water jet technology. The exploratory objective is to use near-infrared images of the wound (taken Snapshot_{NIR}, a specialized near-infrared camera) for the characterization and measurement of tissue oxygenation that could enable correlation of wound tissue oxygenation before and after debridement with micro water jet technology.

Study Design

This is a prospective cohort, single-center, open-label study in subjects with chronic lower extremity wounds. The study will enroll up to 20 subjects. Subjects will undergo screening evaluations to determine eligibility to enroll in the study. All study subjects will receive micro water jet technology debridement as opposed to other debridement methods as part of their wound care treatment. The other aspects of subjects wound care protocol will remain unchanged. In the case of bilateral limb ulcers, or multiple ulcers, subjects will have the option to receive micro water jet debridement on one or all of the ulcers.

Study Population

Patients, male or female age 18 or older, with uninfected, chronic lower extremity ulcers greater than one-month duration that has not adequately responded to conventional ulcer therapy

Length of Study

Up to 20 weeks, sooner pending wound healing as defined by 100% re-epithelialization.

Study Treatments

All study subjects will receive micro water jet technology debridement as opposed to traditional debridement using instruments or other means of debridement. Other aspects of subjects wound care protocol will remain unchanged.

Overview of Efficacy Assessments

The following efficacy assessments will be performed:

- 1. The extent and size of ulcers (summation of the products of the long x short axis for all ulcers measured in centimeters squared, plus ulcer depth) will be evaluated and photographs of ulcers taken during screening and on all clinic visits up to 20 weeks or when the ulcer is healed, whichever is sooner.
- 2. Leg rest pain score VAS graded from 0 (pain free) to Grade 10 (maximum pain) during screening on again on all clinical visits for up to 20 weeks, sooner pending wound healing.
- 3. Pain during Debridement score VAS graded from 0 (pain free) to Grade 10 (maximum pain) during on all clinical visits when debridement is performed for up to 20 weeks, sooner pending wound healing.
- 4. Subjects feedback regarding their debridement experience with micro water jet technology will be collected on all clinical visits when debridement is performed.
- 5. Incidence of wound infection.

The following exploratory assessments may be performed pending availability of near-infrared image camera:

1. Near-infrared image of the wound before and after debridement.

Data and Safety Monitoring Plan

We plan to use the NIDDK 'Data & Safety Monitoring (DSM) Guidelines for Clinical Trials'. The PI will evaluate the data on an ongoing basis and quarterly reports will be prepared to evaluate the progress of the trial (accuracy of data, verifying consent of subjects, and adherence to protocol schedule.). Clinical and patient data will be maintained, segregated and secured in locked filing cabinets only accessible to the Investigators. Patient records will be held as strictly confidential and names, or other identification, will not be used for publication or other purposes. All employees related to this proposal will be certified in accord with the NIH Human Participants Protection Education for Research Teams.

Sample Size Estimation:

Previous work done suggests that a small case series of 16 patients is adequate as a pilot trial. Accounting for a 20% potential fall out rate means that a total of 20 subjects should be enrolled into the study.

Data Analysis

1. INTRODUCTION

Chronic ulcerations are wounds that have failed to properly proceed through the repair process and do not produce functional or anatomic integrity within a three month healing period. The underlying causes of chronic wounds often include venous insufficiency, arterial perfusion, diabetes, unrelieved pressure as well as contributing systemic factors such as immunosuppression, nutrition and infection. Due to a population of increasing age and weight, and the comorbidities of diabetes and venous insufficiency, lower extremity ulcers that are vascular and/or diabetic in nature are the most frequently encountered chronic wounds. The prolonged healing process of chronic ulcerations results in both economic loss and an impaired quality of life for patients that suffer from such wounds. Not only does the management of chronic wounds drain healthcare resources, but failure to manage could lead to even more devastating situations such as sepsis and amputation. The process of t

Debridement is the removal of devitalized or necrotic tissue or foreign bodies from a wound⁵ and is considered by many as the key initial first step in wound healing. Debridement may aid wound healing by removing tissue with the highest bacterial counts, thereby bringing the wound into bacterial balance. Debridement can also activate platelets to release the contents of their alpha granules. The released growth factors stimulate the inflammatory response that is believed to play an important role in wound healing. Optimum debridement should achieve a balance between the removal of necrotic tissue and preservation of healthy tissue and not inhibit subsequent healing⁶. Formation of new granulation tissue following debridement may help to perpetuate the wound-healing cascade

Efficient debridement is an essential step in acute and chronic wound management. Chronic wounds are likely to require ongoing maintenance debridement rather than a single intervention⁷. The underlying pathogenic abnormalities in chronic wounds cause a continual build-up of necrotic tissue, and regular debridement is necessary to reduce the necrotic burden and achieve healthy granulation tissue. Debridement also reduces wound contamination and therefore assists in reducing tissue destruction⁸. Dead spaces that may otherwise harbor bacterial growth must be exposed during debridement. Various methods of debridement are available, each with its own advantages and limitations. The methods that are most efficient at removal of debris may, at the same time, be the most detrimental to fragile new growth, and in many cases, more than one method may be appropriate.

Hydrosurgery has been shown to be an efficient method of wound debridement and wound bed preparation⁹. The technology has been shown to be faster, more precise, and results in less tissue damage than other debridement methods¹⁰. Debritom+ (Medaxis AG, Baar Switzerland) is a hydrosurgery device that utilizes micro water jet technology that has been designed to debride acute and chronic wounds precisely and in a tissue-preserving manner. The system has a 510(k) approval by the FDA and a CE mark in Europe. With this technology, the water jet is fed with pressure through a tube connected to the main device to a non-return nozzle that generates a very fine water jet (Figure 1). The pressure that has been set is equal to the pressure prevailing before the point of entry into the nozzle. A recently published study found the micro water jet to help remove fibrin, necrotic tissue, and foreign bodies while leaving the granulating tissue unharmed allowing for faster wound healing in chronic, stalled wound¹¹. The authors noted that debridement using micro water jet technology can be carried out with no or only minimal pain,

easily eliminated by simple local measures. Furthermore, the micro water jet application removes the need to touch the wound during debridement to minimize possible cross-contamination.

Figure 1. Micro water jet debridement device.

2. STUDY OBJECTIVES

2.1 Primary Objective

The primary objective of this prospective cohort study is to assess the clinical effectiveness of micro water jet technology in the debridement and healing of chronic wounds in terms of wound size, depth/extent, and percent wound reduction and healing. Additional assessments will include evaluating changes in leg rest pain score using a visual analogue scale (VAS); incidence of infection, and pain during debridement via the VAS scale as well as patient feedback regarding their debridement experience with micro water jet technology.

2.2 Exploratory Objective

The exploratory objective is to use near-infrared images of the wound (taken via Snapshot_{NIR}, a specialized near-infrared camera) for the characterization and measurement of tissue oxygenation that could enable correlation of wound tissue oxygenation before and after debridement with micro water jet technology (Section 3.2). Data from the exploratory objective may not be included in the clinical study report.

3. STUDY END POINTS

3.1 Primary Endpoints

The primary endpoints are to explore clinical efficacy and include:

- 1. The extent and size of ulcers (summation of the products of the long x short axis for all ulcers measured in centimeters squared, plus ulcer depth) will be evaluated and photographs of ulcers taken during screening and on all clinic visits up to 20 weeks or when the ulcer is healed, whichever is sooner.
- 2. Leg rest pain score visual analogue scale (VAS) graded from 0 (pain free) to Grade 10 (maximum pain) during screening and on all clinic visits up to 20 weeks, or when the ulcer is healed, whichever is sooner.
- 3. Pain during Debridement score VAS graded from 0 (pain free) to Grade 10 (maximum pain) during on all clinical visits when debridement is performed for up to 20 weeks, sooner pending wound healing.
- 4. Subjects feedback regarding their debridement experience with micro water jet technology will be collected on all clinical visits when debridement is performed.
- 5. Incidence of wound infection.

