4. OVERALL STUDY DESIGN

4.1 Study Design

This is a prospective cohort, single-center, open-label study in subjects with chronic lower extremity wounds. The study will enroll up to 20 subjects. Subjects will undergo screening evaluations to determine eligibility to enroll in the study. All study subjects will receive micro water jet technology debridement as opposed to other debridement methods as part of their wound care treatment. The other aspects of subjects wound care protocol will remain unchanged. In the case of bilateral limb ulcers, or multiple ulcers, subjects will have the option to receive micro water jet debridement on one or all of the ulcers.

Clinical efficacy analyses will include assessment of changes in the extent and size of ulcers, percentage healing and rate of healing, leg rest pain score using VAS scale, pain experience during debridement using VAS scale, incidence of wound infection (See Section 3).

Safety assessments, including AE reporting, physical examination, vital sign measurements, concomitant medications will be performed at all clinical visits throughout the study.

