5.3 Study Participants

20 patients with chronic lower extremity ulcers will be recruited for this prospective cohort at the Rosalind Franklin Health Clinic to receive micro water jet technology debridement as part of their wound care treatment plan after being informed of the study and providing informed consent

Inclusion Criteria and Population:

- a) Male or female age 18 or older
- b) The ability and willingness to provide Informed consent
- c) Presence of a chronic lower extremity ulcer
 - Chronic ulcer is defined as that $\prod 4$ weeks in duration.
 - Subject's informed consent for participation prior to proceeding with micro water jet technology debridement
- d) Patient's ulcer cannot exhibit any gross clinical signs of infection.
- e) Patient is willing to participate in all procedures and follow up evaluations necessary to complete the study.
- f) Patient willing and able to comply with having micro water jet technology debridement potentially weekly or biweekly as part of their wound care treatment plan for up to 20 weeks. Exclusion Criteria:
- a) Patients with active wound infection, or untreated osteomyelitis
- b) Patients with dementia, or impaired cognitive function
- c) Patients who are unable or unwilling to participate in all procedures and follow up evaluations
- d) Patient has Active Charcot foot
- e) Patient with malignant wounds

5.4 Subject events after entry:

Screening/Pre-debridement:

Subjects will be screened to ensure that they meet the inclusion and exclusion criteria. The study will be explained and written informed consent obtained from each patient prior to the initiation of screening procedures.

Following the screening, subjects will receive baseline evaluation/assessment as part of the general clinic visit and treatment initiation. Baseline evaluation/ assessment will include recording of clinical observations.

Clinical Observations and Recording:

1. Wound size and appearance:

Wound dimensions, locations, and characteristics will be documented prior to commencement of the study and assessed weekly or biweekly. Ulcer assessments include wound measurement, photographs, proportion of granulation tissue, and dressing changes.

2. Physical exam:

Physical exam will be conducted, including vascular, dermatological, deformities and range of motion, neurological, and infection assessments, as part of a regular wound care visit.

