5.5 Treatment

Following base assessment, the wound will be debrided using micro water jet technology. An initial test of sterile saline will be sprayed onto the patient's hand so the patient can get a feel for the force of the water jet and know what to expect. Topical analgesic (lidocaine) will be administered to the wound area prior to debridement as needed. Micro water jet technology will be used to remove all devitalized, necrotic tissue and until extremely fine bleeding develops. A protective shield will be used to prevent spread of the aerosol formed after the stream of sterile saline comes into contact with the wound (Figure 4). Both the hand piece delivering the sterile saline stream and the protective shield are one-time use disposable items. Treatment times will be dependent on the wound size and level of contamination. A previously published retrospective study noted the treatment duration to be between 1 and 22 minutes utilizing 100-200mL of sterile saline as rinsing fluid¹¹. Hemostasis will be controlled via pressure. Appropriate wound dressings will then be applied. Caution will be used in patients with uncontrolled hypertension and patients on anticoagulation therapy or acetylsalicylic acid medication. While debridement is not contraindicated in these patients, there may be a higher risk of excessive bleeding. Compression will initially be used to control hemostasis followed by an alginate or a hemostyptic agent.

Figure 4.

Debridement of wound using micro water jet technology. A protective shield is used to prevent the spread of the aerosol formed after the stream of sterile saline comes into contact with the wound.

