5.6 Subsequent visits

Patients will return to clinic every one to two weeks (+/- 2 days) as part of their regular wound care treatment plan for follow up assessment including wound evaluation and photograph. Wounds will be subsequently debrided using micro water jet technology if deemed appropriate by the investigators followed by a dry sterile dressing as previously described. Wound will be followed for a total of 20 weeks or when the wound has completely healed, as defined by 100% re-epithelialization.

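### Primary endpoint 1 sums size over all ulcers although a subject may have the device on only one, so in partly treated subjects the change mixes device-treated and other ulcers

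*Combined protocol and SAP*

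**What the plan says.** - **Endpoint.** Section 3.1, item 1, takes the "summation of the products of the long x short axis for all ulcers measured in centimeters squared" and adds ulcer depth, at screening and at every clinic visit up to 20 weeks or healing. The Protocol Summary (Overview of Efficacy Assessments) repeats this.
- **Treatment.** Section 4.1, and the Protocol Summary under Study Design, state that with bilateral or multiple ulcers "subjects will have the option to receive micro water jet debridement on one or all of the ulcers".
- **Objective.** Section 2.1 aims to "assess the clinical effectiveness of micro water jet technology in the debridement and healing of chronic wounds".
- **Use of the endpoint.** Section 4.1: "Clinical efficacy analyses will include assessment of changes in the extent and size of ulcers, percentage healing and rate of healing".
- **Care of ulcers without the device.** Section 4.1: "The other aspects of subjects wound care protocol will remain unchanged". Section 5.8 gives standard adjunctive therapy to all patients. How an ulcer not chosen for the device is debrided, if at all, is not stated.
- **Analysis.** Section 8.2 lists tests, among them repeated measures analysis of variance, but does not say which ulcers form the outcome.

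**The concern.** The rule for what is measured and the rule for what is treated cover different sets of ulcers. If a subject with several ulcers elects the device on one, the endpoint as written still adds up all of them. The resulting change is then analysed as clinical efficacy, although part of the summed area never received the device.

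At stake is the meaning of the wound-size result, which is listed first among the primary endpoints. The objective asks how wounds fare with micro water jet debridement. A sum that includes ulcers without it answers that question less directly, and a reader of the report could not tell by how much unless the two groups of ulcers were labelled.

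**Working it through.** **1. Does any text narrow the sum?**

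- Section 5.5 says that "the wound will be debrided using micro water jet technology", and Section 5.6 that "Wounds will be subsequently debrided using micro water jet technology if deemed appropriate by the investigators". Both describe the procedure. Neither names an index ulcer or says which ulcers enter endpoint 1.
- Item 1 of Section 3.1 stops measurement when the ulcer, in the singular, is healed, but does not say which ulcer that is.
- Section 4.1 has all subjects receive the device rather than other debridement methods. That is a statement about subjects, and the same paragraph then offers the one-or-all option.
- Section 8.2 is silent.

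So the literal rule stands.

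**2. The plan's own figure.** Section 8.1 gives 16 subjects and 20% fall-out: 16 / (1 − 0.20) = 20, as stated. The documents give no frequency of multiple ulcers, no rate of partial election and no expected healing rate. The inputs below, other than 16, are therefore assumptions.

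**3. One partly treated subject (area only).** Let *s* be the device-treated share of baseline area, *t* the percent reduction in device-treated ulcers and *u* that in the others. The percent reduction in the sum is

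*s·t* + (1 − *s*)·*u*.

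It equals *t* only if *s* = 1 or *u* = *t*. With *s* = 0.5, *t* = 50 and *u* = 10 it is 25 + 5 = 30%, against 50% in the device-treated ulcers.

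**4. The cohort.** Assume that each subject's percent reduction is averaged with equal weight, that *t* = 50 in everyone, and that *k* of 16 are partly treated. The mean is

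*t* − (*k*/16)(1 − *s*)(*t* − *u*).

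With *s* = 0.5:

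| Other ulcers | k = 0 | k = 1 | k = 2 | k = 4 |
|---|---|---|---|---|
| shrink 10% | 50 | 48.75 | 47.5 | 45 |
| grow 10% | 50 | 48.125 | 46.25 | 42.5 |
| shrink 50% | 50 | 50 | 50 | 50 |
| shrink 70% | 50 | 50.625 | 51.25 | 52.5 |

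For example, with *k* = 2 and *u* = 10: 50 − (2/16)(0.5)(40) = 47.5.

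**5. Varying the area share, *k* = 2.** Absolute shift in points:

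| s | u = 10 | u = −10 | u = 70 |
|---|---|---|---|
| 0.7 | 1.5 | 2.25 | 0.75 |
| 0.5 | 2.5 | 3.75 | 1.25 |
| 0.3 | 3.5 | 5.25 | 1.75 |

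Where the two groups of ulcers heal differently, the range is 0.75 to 5.25 points: downward if the other ulcers do worse, upward if they do better. The shift is zero if nobody is partly treated or if both groups heal alike.

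**The case against.** The strongest reply is that this is a wording gap of little consequence.

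- **Intent.** Sections 5.5 and 5.6 speak of the wound that is debrided and followed, so the endpoint may have been meant to cover study ulcers only. That is a possible reading, but no section defines a study ulcer, and the endpoint says otherwise.
- **Size.** The study is an open-label, uncontrolled pilot whose endpoints are exploratory, with no success threshold or powered hypothesis. If the between-subject SD of percent reduction were 20 to 40 points (an assumption), the 95% half-width with 16 subjects would be about 2.13 × SD / 4, or 11 to 21 points. The shifts above lie inside that. This stands and limits the severity. It does not make the stated rule fit the objective, and within a single partly treated subject the difference can be large (30% against 50% in step 3).
- **Choice of measure.** An all-ulcer sum is a legitimate patient-level measure and does not depend on which ulcer the subject chose, whereas a device-treated set is self-selected. This also stands. It is a reason to keep the sum as a secondary summary and to state the selection openly.

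On the other side, a reader might infer that the ulcers without the device are untreated and could serve as within-subject controls. The documents do not support this: those ulcers continue to receive wound care and adjunctive therapy, their debridement is not described, and the subject decides which ulcers get the device.

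**Conclusion.** The point holds for partly treated subjects only. As written, endpoint 1 mixes device-treated and other ulcers in these subjects, and nothing in the documents resolves this.

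The conflict in the text is certain; its effect is not. It may be nil, because the number of partly treated subjects is not given and may be zero. With 2 of 16 partly treated, a 50% reduction in device-treated ulcers and the other assumed values above, the cohort mean shifts by about 1 to 5 points.

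A reader might infer that the sum dilutes the result and so understates the device. The documents do not support a direction: the sum reads higher than the device-treated figure if the other ulcers heal better. Nor do they support the view that the wound-size result is invalid as a whole, since subjects with one ulcer, or with the device on every ulcer, are unaffected.

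Severity: minor to moderate.

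**What to change.** In Sections 3.1 and 8.2 (and the matching summary text):

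1. Record for each ulcer at baseline whether the subject elects it for micro water jet, and at each visit whether the device was used on it. The visit record is needed because Section 4.1 does not say when the option is exercised and Section 5.6 leaves repeat debridement to the investigators.
2. Define the primary size measure, both summed area and depth, on the ulcers elected at baseline. Report any ulcer elected later separately.
3. Keep the all-ulcer sum as a secondary patient-level summary.
4. Report ulcers not treated with the device separately and descriptively, and give the number of partly treated subjects.

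**Cost.** Revised endpoint wording, one baseline field per ulcer and one field per ulcer per visit. No new wound measurement is needed, because Section 5.4 already provides that "Wound dimensions, locations, and characteristics will be documented prior to commencement of the study and assessed weekly or biweekly". The sample size does not change.

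**Limits.** The primary set is chosen by the subject. An ulcer elected at baseline but seldom debrided with the device stays in it, so mixing is reduced and made visible, not removed. With no control group, the change gives a clearer description of device-treated ulcers but does not isolate a device effect.
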